8.4.3.3 Expectedness

The investigator will be responsible for determining whether an AE is expected or unexpected. An AE will be considered unexpected if the nature, severity, or frequency of the event is not consistent with the risk information provided in the IB.

8.4.4 Time Period and Frequency for Event Assessment and Follow-Up

The occurrence of an AE or SAE may come to the attention of study personnel during study visits and interviews of a study subject presenting for medical care, or upon review by a study monitor.

All AEs including local and systemic reactions not meeting the criteria for SAEs will be captured on the appropriate eCRF. Information to be collected includes event description, time of onset, clinician's assessment of severity, relationship to study product (assessed only by those with the training and authority to make a diagnosis), and time of resolution/stabilization of the event. All AEs occurring while on study must be documented appropriately regardless of relationship. All AEs will be followed to adequate resolution.

Any medical condition that is present at the time that the subject is screened will be considered as baseline and will be reported in the Medical History eCRF page, not as an AE. However, if the study subject's condition deteriorates at any time during the study, it will be recorded as an AE.

Changes in the severity of an AE will be documented to allow an assessment of the duration of the event at each level of severity to be performed. AEs characterized as intermittent require documentation of onset and duration of each episode.

The investigator will record all events with start dates occurring any time after informed consent is obtained until 7 days after the study drug administration for non-serious AEs or 30 days after the study drug administration for SAEs. At each study visit, the investigator will inquire about the occurrence of AE/SAEs since the last visit. Events will be followed for outcome information until resolution or stabilization.

8.4.5 Adverse Event Reporting

[Table 7](#) below summarizes the different reporting periods for AEs, SAEs, and pregnancy.

Table 7 Adverse Event Reporting Periods

Type of Event	Adverse Event	Serious Adverse Event / SUSAR	Pregnancy
Reporting period	From consent until 7 days after study drug administration or until AE is resolved or no further follow-up is required. (from consent to dosing, only collect AEs related to study procedures)	From consent until: 30 days after study drug administration or until SAE is resolved or no further follow-up is required	From dosing until 30 days after study drug administration
Reporting Timelines to the Sponsor	Entered into the clinical database on an ongoing basis	Within 24 hours of the investigator's knowledge	Within 24 hours of the investigator's knowledge
Reporting Method	AE eCRF	AE eCRF and SAE form	Pregnancy Form

Abbreviation: AE, adverse event (AE); eCRF, electronic case report form; SAE, serious adverse event ; SUSAR, serious unexpected suspected adverse reaction.

Events that begin before the start of study drug but after obtaining informed consent will be recorded on the AE section of the eCRF and will be identified in the analysis as non-TEAEs.

All SAEs will be recorded and reported to the Sponsor or designee immediately and under no circumstance should this exceed 24 hours from site awareness. The investigator will submit any updated SAE data to the Sponsor or designee within 24 hours of it becoming available.

Investigators are not obligated to actively seek AEs or SAEs after conclusion of a subject's study participation. However, if the investigator learns of any SAE, including a death, at any time after a subject has completed the study, and he/she considers the event to be related to the study drug or study participation, the investigator must promptly notify the Sponsor or designee.

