1.3 SCHEDULE OF ACTIVITIES (SoA)

Table 1 Schedule of Activities (Subjects with Neurodegenerative Diseases, All Dose Cohorts)

Study Procedures	Screening ¹	Treatment	Follow-up	Notes
Study Visit	-42 to -1	Day 1	Day 8/EOS/ET	
Visit window (days)	42		+2	
Informed consent	X			
Domiciled		X ^a		a. Subjects will be admitted to the clinical research unit in the morning for 8 hours confinement
Medical/ocular history/Physical exam	X			On Day 1, PE may be repeated if abnormalities are detected at screening. Relevant ocular and disease-specific history will be captured up to date of diagnosis.
Eligibility (inclusion/exclusion criteria)	X			
Body weight and Height	X			
Eye examination/	X	X	X	Refer to Section 8.1.1.
Color fundus photography	X			
Vital signs	X	X ^b	X	b. To be collected predose, and at 0.25, 0.5, 1, 2, 8 hours postdose. A window of \pm 5 minutes will be allowed for measurements up to 2 hours, and \pm 10 minutes beyond 2 hours.
12-lead safety (ECG)	X	X ^c	X	c. Triplicate at the following timepoints: predose (within 1 hour), and at 90 minutes (\pm 15 minutes) and 8 hours (\pm 60 minutes) postdose or before discharge
Safety laboratories	X	X ^d	X	Refer to Section 10.2. d. To be collected predose on Day 1 and before discharge
Urinalysis	X	X	X	
Pregnancy test	S	U (predose)	U	S = Serum; U = Urine
Adverse event reporting	X	X	X	

Study Procedures	Screening ¹	Treatment	Follow-up	Notes
Study Visit	-42 to -1	Day 1	Day 8/EOS/ET	
Visit window (days)	42		+2	
Concomitant medications	X	X	X	
Retinal fundus fluorescence (FF) imaging		X ^e	X	e. Refer to Section 8.1.2
Retinal optical coherence tomography (OCT) and OCT angiography (OCTA)	X		X	
Blood PK sampling		X ^f		f. On Day 1, PK blood samples will be collected at the following time points: 0 (predose), and at 3, 6, 15, and 30 minutes postdose and 1, 2, 4, 6, and 8 hours postdose. A window of ± 5 minutes will be allowed for samples collected from 30 minutes to 2 hours, and ± 10 minutes beyond 2 hours.
Study drug administration		X		

Abbreviations: AE, adverse events; ECG, electrocardiogram; EOS, end of study; ET, early termination; FU, follow-up; PE, physical examination; PK, pharmacokinetics.

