6.5 TREATMENT OF OVERDOSE

For this study, any dose of AMDX-2011P greater than the assigned dose will be considered an overdose.

There is no specific treatment recommended to treat an overdose of study drug, and the subject should receive treatment directed towards any symptoms manifested.

In the event of an overdose, the investigator/treating physician should:

1. Contact the Study Medical Monitor immediately.
2. Closely monitor the subject for any AE/SAE and laboratory abnormalities until AMDX-2011P can no longer be detected systemically (at least 48 hours).
3. Document the quantity of the excess dose as well as the duration of the overdose in the eCRF.

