7 STUDY DRUG DISCONTINUATION AND SUBJECT DISCONTINUATION/WITHDRAWAL

7.1 STOPPING RULES

The SMC will monitor safety throughout the study. The SMC will meet periodically to review available safety data to make decisions regarding continuation, modification, suspension, or termination of the study.

Study Stopping Rules

Dose escalation or administration of study drug in a dose cohort may be stopped and additional subjects will not receive study drug until a consultation has taken place among the investigator, the Study Medical Monitor (or designee), and SMC if one of the following circumstances occurs in subjects treated with AMDX-2011P unless it is determined by the SMC in consultation with investigator and the Study Medical Monitor that the occurrence is not related to the administration of the study drug:

- Two or more subjects in a cohort experience a Common Terminology Criteria for Adverse Events (CTCAE) Grade 3 or higher clinical or laboratory abnormality that is considered to be related to study drug by the investigator.
- An AE or group of AEs that singularly or in aggregate suggests to the investigator or Sponsor that the study drug is poorly tolerated and further treatment per protocol may not be safe.
- If one or more subject(s) in a cohort experience any treatment-related, treatment-emergent SAEs, dose escalation will be stopped to re-evaluate the dose in question.

If any of these criteria occur, the SMC will review all available data; if an event is determined to be related to a specific dose level, doses in subsequent cohorts may be modified or dose escalation may be terminated. Prior to any required dose level adjustment, the clinical and laboratory safety parameters from the previous dosing cohort(s) will be reviewed and discussed by the SMC to allow a recommendation on advancing to the next dose level. The suggested next doses may be the protocol-defined escalation dose, an equivalent dose, an intermediate dose, or an adjusted-downward dose based on evaluation of safety and tolerability data from previous cohorts.

The Sponsor, investigator, and the IRBs reserve the right to terminate or suspend the study at any time; the reason for such decision must be recorded. Should this occur, all data available will also be recorded in eCRFs. The investigator should notify the IRB in writing of the study's completion or early termination.

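### Non-serious related Grade 3+ events count toward the two-subject hold rule in Protocol 7.1, but Table 7 gives them no reporting deadline, so dosing within a cohort can continue after the rule is met

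*Protocol*

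**What the plan says.** Protocol 7.1 has three triggers. The first is met when "Two or more subjects in a cohort experience a Common Terminology Criteria for Adverse Events (CTCAE) Grade 3 or higher clinical or laboratory abnormality" that the investigator judges related; seriousness is not required. The second is one adverse event, or a group of them, that leads the investigator or Sponsor to think the drug is not well tolerated and further dosing may be unsafe. The third is any related treatment-emergent SAE, after which "dose escalation will be stopped to re-evaluate the dose in question". When a trigger is met, dosing or escalation "may be stopped and additional subjects will not receive study drug until a consultation has taken place", unless the SMC decides that the event is unrelated.

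Section 8.4.3.1 separates severity from seriousness, so a Grade 3 event need not be an SAE. Table 7 in 8.4.5 allows 24 hours for SAEs and pregnancies. The entry for other adverse events is "Entered into the clinical database on an ongoing basis", with no hour or day limit.

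On oversight, 7.1 says "The SMC will meet periodically to review available safety data" and gives no interval. Section 4.1 makes continued dosing within a cohort the default until a rule is met, with a one-hour stagger that applies only within a center. The Synopsis plans four to five sites. The SAP adds nothing on notification.

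**The concern.** The two-subject rule can work only if someone learns of both events in time. If both occur at one site, the investigator there can see that the rule is met. If they occur at different sites, each investigator may know of only one. All sites enter data into one electronic system, so a central count is possible, but nothing supplied says how soon an event must be entered or who checks for a second one.

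The protocol does use a direct route elsewhere: for an overdose the investigator must "Contact the Study Medical Monitor immediately" (6.5). Events that count toward a stopping rule have no equivalent unless they are serious.

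This is a first-in-human study. What is at stake is a few additional subjects dosed at a level that has already met the sponsor's own threshold for pausing.

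**Working it through.** **The texts side by side**

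| Event | Counts toward the two-subject rule? | Reporting limit (Table 7) |
|---|---|---|
| Related SAE, Grade 3+ | Yes; also stops escalation on its own | 24 hours |
| Related Grade 3+ clinical or laboratory abnormality, not serious | Yes | None stated |

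The protocol states no operating characteristic for the rule, so there is no plan figure to reproduce. The size of the gap can be bounded with a simple delay model.

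**Inputs from the protocol.** Cohorts 3 and 4 have 12 subjects; cohorts 1 and 2 have 3 to 9 (Table 3). One subject per cohort is a sentinel, and 4.1 enrols the rest only if no safety issue is seen in that subject. That leaves n = 11, 8 or 2 post-sentinel subjects in cohorts of 12, 9 or 3.

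**Assumptions (not in the documents).** Exactly two qualifying events, at random among the n subjects; k = 1, 2 or 3 doses per day across all sites; a hold in force L further dosing days after the second event is recognised. L = 1 represents a 24-hour notice; L = 2, 3 or 5 represents slower entry.

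**Formula.** Let T be the later of the two recognition days, each being the dosing day plus any detection lag. Subjects left undosed = max(0, n − k(T + L)), averaged over all pairs. The gain is this mean at L = 1 minus the mean at the longer L.

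**Both events recognised on the dosing day, n = 11.** There are 11 × 10 / 2 = 55 pairs. At k = 1, if the later event is in the subject dosed t-th, there are t − 1 pairs and 11 − (t + L) subjects left. For L = 1 the total is Σ(t − 1)(10 − t) = 120 over t = 2 to 10. The other totals are obtained in the same way:

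| L | k = 1 | k = 2 | k = 3 |
|---|---|---|---|
| 1 | 120 | 72 | 39 |
| 2 | 84 | 29 | 6 |
| 3 | 56 | 8 | 0 |
| 5 | 20 | 0 | 0 |

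Gains, in subjects not dosed:

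| Compared with | k = 1 | k = 2 | k = 3 |
|---|---|---|---|
| L = 2 | 36/55 = 0.65 | 43/55 = 0.78 | 33/55 = 0.60 |
| L = 3 | 64/55 = 1.16 | 64/55 = 1.16 | 39/55 = 0.71 |
| L = 5 | 100/55 = 1.82 | 72/55 = 1.31 | 39/55 = 0.71 |

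**Same case, n = 8 (28 pairs).** Mean undosed is 1.25, 0.50, 0.21 at L = 1; 0.71, 0.07, 0 at L = 2; and 0.04, 0, 0 at L = 5, for k = 1, 2, 3. The gains are 0.54, 0.43, 0.21 against two days and 1.21, 0.50, 0.21 against five.

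**Events found late.** After dosing, safety laboratories are scheduled only before Day 1 discharge ("To be collected predose on Day 1 and before discharge") and on Day 8. Adverse events are asked about by visit: "At each study visit, the investigator will inquire about the occurrence of AE/SAEs since the last visit". Subjects other than the sentinel have no scheduled contact in between. Taking Day 8 as five weekday dosing days after dosing, with n = 11:

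- One event recognised on Day 1 and one on Day 8, k = 1 (110 ordered pairs): undosed totals are 70, 38 and 0 at L = 1, 2 and 5. The gains are 32/110 = 0.29 and 70/110 = 0.64.
- Both found on Day 8, k = 1 (55 pairs): totals are 10, 4 and 0. The gains are 6/55 = 0.11 and 10/55 = 0.18.
- At k = 2 or 3 the gain is 0 in both cases.

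**Where the gain is zero.** With n = 2 (a 3-subject cohort), two post-sentinel events leave nobody undosed. If all remaining subjects are dosed on one day, no hold can act. If ordinary data entry already produces a hold after one dosing day, the deadline adds nothing.

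**The case against.** The strongest reply is that other text already covers most of this.

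- The second trigger in 7.1 needs neither a count nor a second subject. One investigator, or the Sponsor, can start the same consultation after a single event.
- Section 8 asks for urgent safety worries to be raised with the Sponsor at once.
- Section 8.2.4 has clinically significant laboratory values repeated until the investigator or Medical Monitor is satisfied, and brings in the Medical Monitor if they do not normalise in reasonable time.
- Many clinical Grade 3 events will also meet the SAE definition and so carry the 24-hour limit.
- Escalation needs SMC review of accumulated adverse events (4.1, 10.1.5).

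All of this is correct, and it narrows the gap mainly to non-serious laboratory values and short-lived clinical events. It does not close it. The first three routes rest on judgement. A single well-tolerated Grade 3 laboratory value that resolves need not prompt a call, yet it is half of the trigger. The last two are firm, but the SAE limit does not reach non-serious events, and the escalation gate does not govern dosing within a cohort.

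A reader might infer that nobody is responsible for the count. The documents do not support that. Section 7.1 has the SMC monitoring safety throughout, the Medical Monitor is a member, and 10.1.5 leaves procedures to a Charter that was not supplied. The Study Reference Manual and data management plan were not supplied either. Any of these may set an entry deadline or assign the tally.

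**Conclusion.** The gap is real in the supplied documents: the plan's slowest reporting route applies to some of the events that its stopping rule counts. It affects continued dosing within a cohort, chiefly when the two events occur at different sites.

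The benefit of closing it is modest. Given two events recognised on Day 1 in a 9- to 12-subject cohort dosed over several days, it is about 0.2 to 1.8 fewer subjects dosed when the alternative is a delay of two to five dosing days. With an event first found on Day 8 it is at most 0.64, and with both at most 0.18, at an assumed pace of at least one dose per day. A slower pace would leave more subjects undosed at Day 8.

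Two stronger readings should be resisted. One is that several subjects would routinely be exposed after the rule is met. The documents give no Grade 3 rate, entry lag or dosing pace, so how often this would matter cannot be estimated. The other is that a missed count lets the study move to a higher dose unchecked; SMC review stands in the way. The hold is also conditional, since 7.1 says dosing may be stopped. This is a low-cost improvement to consider, not a flaw that undermines the study.

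**What to change.** In Table 7 and 8.4.5, require the site to notify the Medical Monitor within 24 hours of awareness of every related Grade 3 or higher clinical or laboratory abnormality, serious or not, through the existing SAE channel. Have the Medical Monitor keep a tally for each cohort and alert all sites when the two-subject rule is met. Add a cross-reference in 7.1. If the SMC Charter, Study Reference Manual or data management plan already provides this, citing it in Table 7 is enough.

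The cost is a few extra expedited reports in a study of up to 36 subjects, one row in Table 7, one sentence each in 8.4.5 and 7.1, and a running tally. Sample size, endpoints and analyses do not change.

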8.4.6 Serious Adverse Event Reporting

The investigator will immediately report to the Sponsor any SAE, whether or not considered study drug-related, including those listed in the protocol or investigator brochure and must include an assessment of whether there is a reasonable possibility that the study drug caused the event. Study endpoints that are serious adverse events (e.g., all-cause mortality) must be reported in accordance with the protocol unless there is evidence suggesting a causal relationship between the study drug and the event (e.g., death from anaphylaxis). In that case, the investigator must immediately report the event to the Sponsor.

All SAEs will be followed until satisfactory resolution or until the site investigator deems the event to be chronic or the subject is stable. Other supporting documentation of the event may be requested by Sponsor and should be provided as soon as possible.

The Sponsor will be responsible for notifying the Food and Drug Administration (FDA) of any unexpected fatal or life-threatening suspected adverse reaction as soon as possible, but in no case later than 7 calendar days after the Sponsor's initial receipt of the information. In addition, the Sponsor must notify FDA and all participating investigators in an Investigational New Drug (IND) safety report of potential serious risks, from clinical studies or any other source, as soon as possible, but in no case later than 15 calendar days after the Sponsor determines that the information qualifies for reporting.

SAE reporting procedures

- The primary mechanism for reporting an SAE to the Sponsor will be the EDC system.
- Investigators will report all SAEs occurring during the study to the contract research organization (CRO) within 24 hours following the site's knowledge of the SAE. All SAEs will be reported using the Serious Adverse Event Report form (SAE Report) in the electronic data system, Medrio. In case that the outcome is death, the investigator will also contact the Medical Monitor via telephone as soon as possible.
- After the study is completed at a given site, the electronic data collection tool will be taken off-line to prevent the entry of new data or changes to existing data.

- If a site receives a report of a new SAE from a study subject or receives updated data on a previously reported SAE after the electronic data collection tool has been taken off-line, then the site can report this information via contact to the Medical Monitor.
- If the electronic system is unavailable, then within 24 hours, the site will contact the Medical Monitor to report the event or email or fax the SAE form as detailed below.
- Contacts for SAE reporting: [contact]

8.4.7 Reporting Events to Subjects

Subjects will be informed about new risks and safety information through updated informed consent during the study.

8.4.8 Reporting of Pregnancy

- Details of all pregnancies in female subjects and of female partners of male subjects will be collected as outlined in Section [10.2](#).
- If a pregnancy is reported, the investigator should inform the Sponsor within 24 hours of learning of the pregnancy and should follow the procedures outlined in Section [10.3.3](#).
- Abnormal pregnancy outcomes (e.g., spontaneous abortion, fetal death, stillbirth, congenital anomalies, ectopic pregnancy) are considered SAEs.

9 STATISTICAL CONSIDERATIONS

9.1 SAMPLE SIZE DETERMINATION AND STATISTICAL HYPOTHESES

This clinical study is designed to explore safety and preliminary activity of AMDX-2011P. A total sample size of ~36 subjects and assuming approximately 10% subjects are false negative, the study will provide test sensitivity and test specificity of approximately 0.8 for each individual subject population and the pooled populations. The study will enroll up to 36 subjects with confirmed diagnosis of Parkinson's disease, MSA or ALS (approximately 12 subjects); the prevalence of disease is assumed at 0.5 for each individual disease population.

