Mutagenicity	AMDX-2011P and AMDX-2011 were mutagenic in bacteria only in the presence of an exogenous metabolic system, suggesting a metabolite was the mutagenic and not the parent drugs. AMDX-2011P and AMDX-2011 did not cause chromosomal aberrations in mammalian cells with or without metabolic activation.	Healthy volunteers are excluded from clinical studies until additional information on human risk is obtained.

Potential Risks which may be associated with Study Procedures

Injection site reactions (ISRs) such as redness, swelling, itching and tenderness	As with any IV administration procedure, ISR is possible. ISRs were seen in nonclinical studies (rats)	IV administration will be done by trained personnel. In the case of ISRs, observe and treat as needed.
Retinal imaging.	Potential mild discomfort, fatigue and temporary dry eyes	For temporary dry eyes, artificial tears may be used to alleviate the symptoms. Retinal imaging will be performed by trained personnel to minimize the time of data acquisition.

Abbreviations: ECG, electrocardiogram; hERG, human Ether-à-go-go-related gene; ISR, injection site reaction; IV, intravenous

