5 STUDY POPULATION

5.1 INCLUSION CRITERIA

Subjects are eligible to be included in the study only if they meet the criteria relevant to their disease status:

Type of Subject and Disease Characteristics

Subjects with Parkinson's Disease

1. Clinically established Parkinson's disease based on Movement Disorder Society (MDS) Clinical Diagnostic Criteria for Parkinson's disease (Table 9) and a modified Hoehn & Yahr scale of 1-3 (Table 10).
2. No suspected atypical parkinsonian syndromes due to drugs, metabolic disorders, encephalitis, or degenerative diseases.

Subjects with ALS

3. Confirmed diagnosis of ALS with both upper and lower motor neuron involvement (Table 11).

Subjects with MSA

4. Diagnosis of clinically established MSA according to MDS 2022 Criteria (Wenning, 2022); refer to Appendix 4, Section 10.4.2.

Age, Gender, Informed Consent, Pregnancy and Contraception

5. Male and female subjects 18 years and older at the time of signing the informed consent.
6. Ability to undergo retinal imaging.
7. Subject or legally authorized representative must provide signed informed consent (or signed assent form) prior to study entry and have the ability and willingness to attend and comply with the necessary study procedures and visits at the study site. For subjects unable to physically sign the informed consent, a guardian or trusted care giver can sign on their behalf in presence of an independent witness.

Contraception

8. Contraception use by study subjects of childbearing potential (male and female) and female partners of childrearing potential male subjects should be consistent with local regulations regarding the methods of contraception for those participating in clinical studies. For details, refer to Section 10.2.
9. Female subjects of childbearing potential and female partners of childbearing potential male subjects must refrain from oocyte donation for up to 30 days after study drug administration.

10. Male subjects must refrain from sperm donation for 90 days after study drug administration.
11. Females of childbearing potential must have a negative serum pregnancy test at Screening and a negative urine pregnancy test on Day 1 (predose). Females not of childbearing potential must be surgically infertile or postmenopausal (defined as cessation of regular menstrual periods for at least 12 months) at Screening.

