9.3 STATISTICAL ANALYSES

9.3.1 General Approach

A formal statistical analysis plan (SAP) and data management plan will be developed and finalized before study database lock. The following is a summary of statistical approach:

- Variables used for sample size calculation will be calculated and presented for pooled populations and each subject population.
- All disposition, demographic, baseline characteristic and concomitant medication summaries will be presented by arm.
- Continuous variables: Descriptive statistics will include the number of non-missing values (n), arithmetic mean, standard deviation (SD), median, minimum and maximum

values. 90% Confidence Intervals (CIs), least-square (LS Means) values and Ratio for Geometrics LS means will also be displayed when appropriate.

- Categorical variables: Descriptive statistics will include counts and percentages per category. The denominator in all percentage calculations will be the number of subjects in the relevant analysis population with non-missing data, unless specifically stated otherwise. Percentages will be displayed to one decimal place. Proportions will be displayed to 3 decimal places.

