10.4.3 ALS Diagnostic Criteria

Table 11 ALS Diagnostic Criteria

Definite ALS	Presence of upper motor neuron and lower motor neuron signs in the bulbar region and at two of the other spinal regions
Probable ALS	Presence of upper motor neuron and lower motor neuron signs in at least two regions with upper motor neuron signs rostral to lower motor neuron signs
Probable ALS, laboratory results supported	Presence of upper motor neuron and lower motor neuron signs in one region with evidence by EMG of lower motor neuron involvement in another region
Possible ALS	Presence of upper motor neuron and lower motor neuron signs in one region or upper motor neuron signs in two or three regions, such as monomelic ALS, progressive bulbar palsy, and primary lateral sclerosis

ALS, amyotrophic lateral sclerosis; EMG, electromyography.

Source: [\(Brooks, 2000\)](#)

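### Protocol 9.1 states a specificity of about 0.8 and assumes a prevalence of 0.5, but the study enrolls only diagnosed patients, so specificity cannot be estimated and both documents' prevalences contradict the sample

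*Protocol*

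**What the plan says.** Protocol 9.1 takes about 36 subjects and about 10% false negatives, and concludes that "the study will provide test sensitivity and test specificity of approximately 0.8 for each individual subject population and the pooled populations". It continues: "The study will enroll up to 36 subjects with confirmed diagnosis of" Parkinson's disease, MSA or ALS, and then "the prevalence of disease is assumed at 0.5 for each individual disease population".

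No disease-free group exists elsewhere in the plan. Protocol 5.1 admits only patients, for example "Confirmed diagnosis of ALS with both upper and lower motor neuron involvement" and "Diagnosis of clinically established MSA according to MDS 2022 Criteria". The mutagenicity row of Table 2 (protocol 2.3.1) adds: "Healthy volunteers are excluded from clinical studies until additional information on human risk is obtained".

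Protocol 9.3.3 defines a positive (any new hyper-fluorescent puncta after injection) and a false negative. SAP 6.8 defines a true positive and a false negative. Neither defines a true negative or a false positive.

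Protocol 9.3.1 commits to reporting: "Variables used for sample size calculation will be calculated and presented for pooled populations and each subject population".

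SAP 3.1 claims sensitivity of at least 0.8 and no longer mentions specificity. It keeps prevalence 0.5 per disease, adds 0.75 pooled, and still describes all subjects as having a confirmed diagnosis.

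**The concern.** Specificity is the share of disease-free subjects who test negative. A study that enrolls only patients has no such subjects, so it can neither provide nor estimate a specificity, whatever its size. A prevalence below 1.0 contradicts the same paragraph's description of the sample.

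Two things are at stake. A specificity of 0.8 in the sample size section could be quoted as a property of the design. And protocol 9.3.1 promises to present the sample-size variables pooled and per disease; if that includes specificity or prevalence, the tables cannot be filled meaningfully. What the trial can deliver is a detection rate among diagnosed patients, and within one disease that rate will be imprecise.

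**Working it through.** **Inputs.** N about 36, false negatives about 10% and prevalence 0.5 per disease (protocol 9.1); prevalence 0.75 pooled and 0.5 per disease (SAP 3.1); disease-free subjects enrolled: 0 (protocol 5.1, Table 2, 9.1). Neither document gives a formula, a confidence level for the 0.8, or a false-positive rate.

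**Step 1: reproduce the 0.8 sensitivity (inferred reading 1).** Take the 10% as a share of all subjects. Then sensitivity = (prevalence − 0.10)/prevalence = 1 − 0.10/prevalence.

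| Prevalence | Sensitivity | Disease-free if applied to all 36 |
|---|---|---|
| 0.5 | 1 − 0.10/0.5 = 0.80 | 36 × 0.5 = 18 |
| 0.75 | 1 − 0.10/0.75 = 0.87 | 36 × 0.25 = 9 |
| 1.0 (actual design) | 1 − 0.10/1.0 = 0.90 | 0 |

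The 0.8 appears only at prevalence 0.5. If the 10% is instead a share of diseased subjects, sensitivity is 0.90 at any prevalence.

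**Step 2: specificity.** Specificity = (1 − prevalence − false-positive share)/(1 − prevalence). At prevalence 0.5, a value of 0.8 needs a further 10% of all subjects to be false positives: (0.5 − 0.1)/0.5 = 0.8. Neither document assumes that. At prevalence 1.0 the expression is 0/0.

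**Step 3: could something else serve as the control?**
- *Another disease group.* A positive is any new puncta, whichever protein causes it, and deposits are sought in all three diseases. A finding in an ALS patient cannot be both the intended detection and a false positive for Parkinson's disease. Nor can three diseases each make up 0.5 of one sample, since 3 × 0.5 = 1.5.
- *The predose image.* It is the reference that decides which puncta are new, so it is not itself a test result.

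**Step 4: read 0.8 as a lower confidence limit around 0.90 (inferred reading 2).** Wald lower limit = 0.90 − z × √(0.90 × 0.10/n), counted per subject, with z = 1.645 (90%) or 1.960 (95%).

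| n | 90% | 95% |
|---|---|---|
| 36 | 0.82 | 0.80 |
| 18 | 0.78 | 0.76 |
| 12 | 0.76 | 0.73 |
| 9 | 0.74 | 0.70 |

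This fits the pooled sample. It does not fit a disease group of 9 or 12 subjects, and it says nothing about specificity.

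**Step 5: realistic precision.** Exact (Clopper-Pearson) two-sided 90% intervals, per subject, as examples only: 8/9, 0.57 to 0.99; 11/12, 0.66 to 1.00; 32/36, 0.76 to 0.96.

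**The case against.** The best defence is that little depends on this text. The study is exploratory, its primary endpoint is safety, SAP 6 plans no formal inference, and the SAP has already dropped specificity and plans no analysis of it. That stands, and it limits the seriousness. It does not cure protocol 9.1, which still states the figure, or SAP 3.1, which still carries the prevalences. Whether SAP 1.1 should list the dropped specificity is a matter of preference.

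A second defence is that the sensitivity claim may be sound: the cases-only value of 0.90 satisfies the SAP's wording of at least 0.8. That is fair as far as it goes. With no method printed, the 0.8 sensitivity cannot be called wrong, only underived.

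Three stronger inferences should be resisted.

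- *No disease group is large enough for a lower limit of 0.80.* Per subject, reading 2 needs 0.09 × (1.645/0.10)² = 24.4, so 25, at 90%, or 0.09 × (1.960/0.10)² = 34.6, so 35, at 95%. But protocol 9.3.3 and SAP 6.8 define a false negative per eye. If Parkinson's disease made up the rest of 36, it would have 15 or 18 subjects, hence 30 or 36 eyes. Ignoring correlation between eyes, these give limits of 0.81/0.79 or 0.82/0.80. The inference holds only if the unit is the subject.
- *A Parkinson's or MSA eye can never be a false negative.* The definition requires a definite diagnosis. Definite is a named grade only in the ALS table ("Presence of upper motor neuron and lower motor neuron signs in the bulbar region" and two further regions), while Parkinson's disease and MSA enter as clinically established. But protocol 9.1 calls all three confirmed, and definite can be ordinary wording for the same thing. The word needs replacing; the documents do not support the stronger conclusion.
- *The plan fixes the number of Parkinson's subjects.* Neither 15 nor 18 is printed; they are 36 − 12 − 9 and 36 − 9 − 9. The total is not firm either: the cohort rows sum to 3 + 3 + 12 + 12 = 30 up to 9 + 9 + 12 + 12 = 42.

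**Conclusion.** The point holds. Protocol 9.1 states a specificity that this design cannot produce: there are 0 disease-free subjects, against 18 of 36 if prevalence 0.5 were applied to the whole sample, or 9 of 36 under the SAP's pooled 0.75. The prevalence contradiction is in both documents; the specificity claim is in the protocol only.

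The sensitivity of 0.8 has no printed derivation. Reading 1 needs disease-free subjects who are not enrolled. Reading 2, per subject, supports about 0.8 for the pooled 36 but not for a group of 9 (0.70 to 0.74). Both readings are inferred. The precision figures assume that every enrolled subject is evaluable for imaging and that the true detection rate is about 0.90.

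This should be fixed, but it does not threaten the trial: safety, escalation and the descriptive analyses stand as planned.

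**What to change.** - **Protocol 9.1:** delete the specificity claim and the 0.5 prevalence. **SAP 3.1:** delete the 0.5 and 0.75 prevalences. In both, state that only a detection rate (sensitivity) among diagnosed subjects can be estimated, assume about 0.90, and give its expected precision at the agreed group sizes with the confidence level stated.
- **Group sizes:** first reconcile the ALS number (about 12 in the Synopsis and 9.1; about 9 in protocol 4.1 and SAP 3). Then recompute the intervals; those above are examples. Do not print Parkinson's counts obtained by subtraction as planned numbers.
- **Protocol 9.3.1:** limit the reported sample-size variables to the detection and false-negative rates. Make SAP 6.8, which presents the diagnostic summary overall, agree on pooled versus per-disease reporting.
- **Protocol 9.1, 9.3.3 and SAP 6.8:** use one unit, subject or eye, and replace the definite-diagnosis wording with the diagnosis required at enrollment.

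The cost is text changes, a protocol amendment with IRB review, possibly one added set of by-disease rows, and loss of the stated specificity. No additional patients or visits are needed.
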